5.5.4 Follow-up of Study Subjects Who Discontinue Device Use

Discontinuation of study device use does not constitute discontinuation from the study, and the study procedures for early termination should be completed as indicated by the SOA (Table 3). If a clinically significant finding is identified, including, but not limited to, changes from baseline, after enrollment, the participating clinical trial site PI or qualified designee will determine if any change in subject management is needed. Any new clinically relevant finding will be reported as an AE.

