1.1.4 Study Key Characteristics

Study Phase

- I

Study Population

- Twenty-five (25) males and non-pregnant females, 18 to 45 years of age, inclusive, who are in good health and meet all eligibility criteria will be enrolled.

Sites

- Carolina Phase I, Raleigh, NC

RD19 Device

- The EmitBio™ RD19 device emits visible blue light to stimulate host defenses (as explained below) and eliminate invading pathogens in the oropharynx and surrounding tissues. The RD19 device does this without additional photosensitizers or chemical reagents that are typically employed with traditional photodynamic therapies. Specifically, selected wavelengths of light have been evaluated across the visible spectrum, and it was discovered that a narrow wavelength band blue light emitted from non-coherent LED sources could perform both of the following functions: upregulate the sustained production of nitric oxide in epithelial tissue through the increase of NO synthases (NOSs); and stimulate the instantaneous release of the body's bound stores of nitric oxide. Nitric oxide also induces and recruits effector cells of the innate immune system, including natural killer (NK) cells, neutrophils and macrophages to phagocytize virus-infected cells at the site of primary infection.

Table 2: Treatment Group

| Group | RD19 | Duration |
|-------|------|------------|
| OL | 25 | 3' x 2/day |

Study Duration

- The duration of the entire study is anticipated to be \leq 18 days (from start of screening to last subject last visit).

Subject Duration

- The duration on trial for each individual subject is \leq 18 days (from start of screening to last visit).

Safety

- The study will use study pausing rules
- This study will involve the Sponsor's Chief Medical Officer as medical monitor, who along with the study PI(s) will assess severe AEs and SAEs, and together will constitute the attribution team.

1.2 Schedule of Activities (SOA) - Table 3

| Study Procedures | Screening Visit | Preliminary Observation | Full Assessment Period | |
|------------------------------------|-----------------|---|---|---|
| Study Day | ≤ -7 to 0 | 1 | 7 | Day 14/ Early Term |
| Study Procedures | | | | |
| Informed Consent | X | | | |
| Inclusion/Exclusion Criteria | X | X | | |
| Demographics Questionnaire | X | | | |
| Medical History | X | * Changes since last visit only | *Changes since last visit only | *Changes since last visit only |

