| Physical Examination | X | *Targeted only | *Targeted only | *Targeted only |
| BMI | X | | | |
| Vital Signs | X | X | X | X |
| Methemoglobin | X | *Before and 60 minutes after device use | *Before and 60 minutes after device use | *Before and 60 minutes after device use |
| Lab Sample Collection & Processing | X | | | X |
| CBC and differential | X | | | X |
| CMP | X | | | X |
| Urinalysis | X | | | X |
| Urine Pregnancy Test | X | | | X |
| Concomitant Medication History/New | X | X | X | X |
| Device Illumination | | X | X | X |
| Acceptability Assessment of Device | | X | X | X |
| Distribution and train diary card | | X | | |

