5.5 Device Discontinuation

5.5.1 Study Pausing Criteria

RD19-01-3Q20 will be paused if any of the following events occur:

- Any subject experiences an SAE after use of the RD19 Device that is considered related to RD19.
- Any subject experiences laryngospasm, bronchospasm or anaphylaxis within 2 hours after use of the RD19 Device that is considered related to RD19.
- Two (2) or more subjects experience an allergic reaction such as generalized urticaria (defined as occurring at three or more body parts) within 72 hours after administration of light that is considered related to RD19.
- Three (3) or more subjects experience a \geq Grade 3 AE (systemic and/or clinical laboratory abnormality), in the same SOC grouping of Preferred Terms based on the Medical Dictionary for Regulatory Activities (MedDRA) coding, considered to be related to RD19.

Study device use and enrollments may resume only after review of the AEs that caused the pause results.

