5.5.3 Investigator Decision to Discontinue Subject Use of Device

A subject may be removed from the study for the following reasons post initial device use; however, whenever possible the subject should be followed for safety evaluations per protocol:

- Study non-compliance to protocol requirements that in the opinion of the participating clinical site PI or appropriate sub-investigator poses an increased risk (e.g., missing safety labs) or compromises the validity of the data.

- Lost to follow-up. (*A subject will be considered lost to follow-up if he or she fails to appear for a follow-up assessment. Extensive effort (i.e., generally three documented contact attempts via telephone calls, e-mail, etc., made on separate occasions) will be made to locate or recall the subject, or at least to determine the subject's health status. These efforts will be documented in the subject's study file.*)
- Medical disease or condition, or new clinical finding(s) for which continued participation, in the opinion of the participating clinical site PI or appropriate sub-investigator, might compromise the safety of the subject, interfere with the subject's successful completion of this study, or interfere with the evaluation of safety.
- If any AE, clinical laboratory abnormality or situation occurs such that continued participation in the study would not be in the best interest of the subject.
- The occurrence of a SAE.
- If the subject is using the device in any manner inconsistent with instructions and protocol directives and procedures.

If the subject agrees, every attempt will be made to follow all AEs through resolution or stabilization.

Subjects who withdraw, or are withdrawn from this study, or are lost to follow-up after signing the informed consent form (ICF) and use of the RD19 device will not be replaced. Subjects who withdraw, or are withdrawn from this study, or are lost to follow-up after signing the ICF but before use of the device may be replaced.

The reason for subject discontinuation or withdrawal from the study will be recorded on the appropriate e-CRF.

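### Subjects taken off the device are sent to an exit visit whose schedule includes another illumination, with no written exemption

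*Combined protocol and SAP*

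**What the plan says.** Section 5.5.4 distinguishes stopping the device from leaving the study. For a subject who has stopped, it says that "the study procedures for early termination should be completed as indicated by the SOA (Table 3").

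Table 3 (Section 1.2) has four visit columns: screening, Day 1, Day 7 and a combined column headed "Day 14/ Early Term". The illumination row reads "Device Illumination | | X | X | X", so the last mark falls in the combined column. The methemoglobin entry there is "Before and 60 minutes after device use".

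Section 5.5.3 lists reasons for removal. One is an adverse event, laboratory abnormality or situation "such that continued participation in the study would not be in the best interest of the subject". Another is misuse: "If the subject is using the device in any manner inconsistent with instructions and protocol directives and procedures". Any SAE, related or not, is also on the list. Section 5.5.2 asks voluntary withdrawals to come back for an early-termination visit.

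Section 5.5.1 gives the study-wide pause. One of its single-subject triggers is "Any subject experiences an SAE after use of the RD19 Device that is considered related to RD19". Once triggered, "Study device use and enrollments may resume only after review of the AEs that caused the pause results".

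**The concern.** The rule for stopping the device and the schedule for the exit visit contradict each other. Followed as written, the schedule re-exposes a subject whose device use was ended, sometimes for safety. Avoiding that depends on the clinician departing from the table. Section 8.1.8 defines any non-compliance with the protocol as a deviation to be reported, so the sensible decision to withhold the light could itself be logged as one.

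If the light is withheld, two other entries lose their anchor. The methemoglobin pair is defined by device use, and Section 6.2 places the acceptability survey in the hour after in-clinic use.

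**Working it through.** There is no stated figure to reproduce. The check sets the sections side by side.

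**1. Which column applies.** Section 5.5.4 points to early-termination procedures in Table 3. Only the column shared with Day 14 fits that description.

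**2. What the column contains.** Twelve rows have an entry: medical history, physical examination, vital signs, methemoglobin, laboratory sample collection, CBC, CMP, urinalysis, pregnancy test, concomitant medication, device illumination and acceptability. Three are tied to device use (methemoglobin pair, illumination, acceptability), and 12 − 3 = 9 are not. The exit visit therefore has a clear purpose without the device.

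**3. Whether an exemption exists.** Neither Table 3, Sections 5.5.1 to 5.5.4 nor Section 6.2 says to omit illumination, or to re-time methemoglobin, for a subject already off the device. The illumination row is intact in the text, so the mark is not an extraction fault.

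**4. Whether the pause closes the gap.** The triggers in 5.5.1, all requiring relatedness to RD19, are:

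| Event | Subjects needed to pause |
|---|---|
| SAE | 1 |
| Laryngospasm, bronchospasm or anaphylaxis within 2 hours of use | 1 |
| Allergic reaction such as generalized urticaria within 72 hours | 2 |
| Grade 3 or higher systemic or laboratory event, same SOC | 3 |

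Section 5.5.3 gives six reasons for removal: non-compliance, loss to follow-up, a medical condition or new finding, an adverse event or laboratory abnormality, an SAE, and device misuse. All except loss to follow-up can lead to an exit visit, so 6 − 1 = 5.

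Subjects who can be removed without triggering a pause include:

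- one subject with an unrelated SAE;
- one with related, non-serious generalized urticaria;
- one or two with a related, non-serious Grade 3 systemic or laboratory event;
- one with a non-serious local reaction. The Grade 3 trigger is limited to systemic and laboratory events, yet illumination-site pain, erythema and edema are solicited events in 6.2.2;
- one with a new medical condition, and one who misused the device.

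Voluntary withdrawals who return under 5.5.2 are also outside the pause.

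**5. Size of the exposure.** Section 2.1.1 gives about 9 J/cm² per use and about 18 J/cm² per day. One exit illumination is 9 / 18 = 50% of a day's dose, where it should be zero.

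**6. Effect on planned analyses if the light is withheld.** Section 7.4.1 summarizes methemoglobin by severity and as the maximum over the study, so the post-use reading is not needed and a single exit reading suffices. Section 7.4.2 analyses acceptability only in the modified per-protocol and per-protocol sets, and 7.3 requires staying on study to at least the Day 7 visit. Survey timing therefore reaches an analysis only for subjects who stop after Day 7 and otherwise qualify.

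**The case against.** The strongest reply is that nobody would read the table this way. Section 5.5.4 is about follow-up after device use has stopped, so taking its cross-reference as an order to use the device again defeats its own premise. Section 5.5.3 says removed subjects should be followed for safety evaluations, and illumination is the intervention, not an evaluation. Section 6.2 ties in-clinic device administration to Days 1, 7 and 14, but names early-termination visits when it lists oropharyngeal examinations. That contrast suggests the mark belongs to Day 14 and the shared column is shorthand. In addition, 5.5.4 lets the investigator change management after a clinically significant finding, 6.2 gives the study clinician all medical decisions, and a subject may decline. On this view the point is an editorial inconsistency, and counts of rows and reasons measure no risk or bias.

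Most of this stands as evidence of intent and as a reason to expect the light to be withheld. The counts do show only the extent of the conflict, not a risk estimate. But none of these texts exempts anyone, and the schedule still says the opposite of what was probably meant. The objection limits the severity; it does not remove the conflict.

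**Conclusion.** The concern holds, as a minor point. Section 5.5.4 and Table 3 conflict as written, and the 5.5.1 pause protects only some of the subjects concerned. The cost per affected subject is one unnecessary illumination of about 9 J/cm². The number affected is unknown and probably small, since Section 7.2 assumes that all 25 subjects will likely complete. No primary estimate is shown to change, and the effect on the acceptability analysis is confined to the few who stop after Day 7.

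This rests on two assumptions: that the column is read literally, and that Appendices 1 and 2, which were not available for this review, contain no exemption.

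**What to change.** Split the combined column, or add a footnote to Table 3 and repeat it in 5.5.4, along these lines:

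> No device illumination is given at an early-termination visit to a subject whose device use has been stopped; a single methemoglobin reading is taken and the acceptability survey is completed without device use.

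Amend the survey-timing sentence in 6.2 to match. The cost is one footnote and one sentence in each of 5.5.4 and 6.2. No visit or test is added, and these subjects are spared one illumination and its 60-minute observation.

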6. STUDY ASSESSMENTS AND PROCEDURES

6.1 Screening Assessments

6.1.1 Screening Procedures

There is a small amount of risk to subjects who report that they are in good health but have an unknown health problem at the time of screening. At the screening visit, and prior to any other study-related activities, the participating clinical site PI or appropriate sub-investigator will provide the subject with detailed study information and will obtain written informed consent.

Some or all of the following assessments are performed during the screening visit to determine eligibility requirements as specified in the inclusion and exclusion criteria:

- Obtain medical history focusing on conditions per protocol exclusion criteria.
- Review pre-study medications and therapies up to 10 days prior to the start of screening that could impact the use of, or response to, the device and record on the appropriate e-CRF.
- Measure vital signs (HR, BP, and oral temperature) and height and weight for determination of BMI.
- Perform full physical examination which will include assessments of the following organs and organ systems: skin, head, ears, eyes, nose, and throat (HEENT), neck, lungs, heart, liver, spleen, abdomen, extremities, lymph nodes (axillary and cervical), and nervous system.
- Obtain blood and urine for clinical screening laboratory evaluations:
 - Hematology
 - CBC with differential
 - Methemoglobin level (Pulse Ox method)
 - CMP (fasting or non-fasting)
 - Urine pregnancy test (in women of childbearing potential)
- Review inclusion and exclusion criteria.

Clinical screening laboratory evaluations will be performed locally by the site laboratory.

The overall eligibility of the subject to participate in the study will be assessed once all screening values are available. The screening process can be suspended prior to complete assessment at any time if exclusions are identified by the study team.

Study subjects who qualify for inclusion will be scheduled for enrollment and their day 1 visit.

If a physiologic parameter, e.g., vital signs or clinical laboratory value, is outside of the protocol-specified range, then the measurement may be repeated once if, in the judgment of the participating clinical site PI or appropriate sub-investigator, the abnormality is the result of an acute, short-term, rapidly reversible condition (e.g., stress, anxiety or “white coat syndrome”) or other source of error. A physiologic parameter may also be repeated if there is a technical problem with the measurement caused by malfunctioning, or an inappropriate measuring device (i.e., inappropriate-sized BP cuff).

A subject may be re-screened if there is a transient disease status (e.g., subject complained of a “cold or fever” and met a temporary delaying enrollment criterion of acute illness or fever), or if a protocol eligibility criterion that is not met at the initial time of screening, will be met by rescreening within the next 2 days.

No subjects may be screened more than twice due to a screening failure result as defined above.

Subjects will be provided the results of abnormal clinical laboratory test values or abnormal clinical findings necessitating follow-up with their primary care provider.

6.1.2 Procedures to be Followed in the Event of Abnormal Clinical Laboratory Test Values or Abnormal Clinical Findings

If a physiologic parameter, e.g., vital signs, or clinical laboratory value, is outside of the protocol-specified range, then the measurement may be repeated once if, in the judgment of the participating clinical trial site PI or appropriate sub-investigator, the abnormality is the result of an acute, short-term, rapidly reversible condition (e.g., stress, anxiety or “white coat syndrome”) or other source of error. A physiologic parameter may also be repeated if there is a technical problem with the measurement caused by malfunctioning, or an inappropriate measuring device (i.e., inappropriate-sized BP cuff).

All abnormal clinical findings or abnormal clinical laboratory tests values that occur post RD19 device use will be considered AEs.

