4. STUDY POPULATION

Twenty-five (25) males and non-pregnant females, 18 to 45 years of age inclusive, who are in good health and meet all eligibility criteria will be enrolled. The target population should reflect the community at large. The estimated time from initiation of enrollment to completion of the day 1 visit for the last subject enrolled is one week.

Subject Inclusion and Exclusion Criteria must be confirmed by a study clinician, licensed to make medical diagnoses and signatory to The Statement of Compliance as the site PI. Exemptions will be only be granted on Subject Inclusion or Exclusion in rare instances and based on the approval of the Sponsor's Chief Medical Officer.

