7. STATISTICAL CONSIDERATIONS

7.1 Statistical Hypotheses

This is a phase I, open-label, safety study and is not designed to test any statistical hypotheses. Rather, this is a descriptive study intended to obtain preliminary estimates in healthy adults of the safety, including reactogenicity, of the EmitBio™ RD19 Device.

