7.2 Sample Size Determination

SAMPLE SIZE CONSIDERATION - OPEN LABEL

This study is designed as an open-label study, without a placebo arm. Given the small sample size, the use of a placebo group is unlikely to improve understanding of AEs. Additionally, having the study unblinded will facilitate the need for rapid review and dissemination of study data for public health reasons.

Rare AEs are not demonstrable in a clinical study of this size; however, the probabilities of observing one or more AEs given various true event rates are presented in the table below. With the assumption that all enrolled subjects will likely complete the trial and safety visits in this relatively short duration study, the following statistical considerations apply. With 25 subjects, the chance of observing at least one AE of probability 20% or more is approximately 97%. Therefore, if no AEs of a given type occur in the study, we can be 97% confident that they will occur in fewer than 20% of people once RD19 is implemented. Also with 25 subjects, the chance of observing at least one AE of probability 5% or more is 90%. Therefore, if no AEs of a given type occur in the study, we can be 90% confident that such adverse event will occur in fewer than 5% of people once RD19 is implemented.

| N | “True” Event Rate | Probability of Observation (%) |
|---|-------------------|--------------------------------|
| 2 | 0.1% | 2.5 |
| | 0.5% | 12.0 |
| | 1.0% | 23.4 |
| | 2.0% | 43.4 |
| | 3.0% | 61.3 |
| | 4.0% | 74.8 |
| | 5.0% | 90.3 |
| | 10.0% | 92.4 |
| | 15.0% | 94.3 |
| | 20.0% | 97.5 |

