7.4 Statistical Analyses

7.4.1 Primary Safety Analyses

Summaries and analyses of safety data will be presented for the Safety Analysis Population.

Solicited AEs will be summarized overall and by maximum severity post through study day 7, post study period days 7 -14 and overall. Additionally, solicited AEs will be analyzed by taking the most severe response (grouped as either modified per protocol or per protocol), dichotomizing into a binary variable (none versus mild, moderate, or severe) and using standard techniques, such as exact confidence intervals (CI), to summarize the proportion of subjects reporting each solicited sign or symptom.

Unsolicited non-serious AEs will be collected from the time of first device use through study day 14. Unsolicited AEs will be coded by MedDRA™ for preferred term and system organ class (SOC). All SAEs will be collected from the time of first device use through the study day 14. The number of SAEs will be reported by detailed listings showing the event description, MedDRA™ preferred term and SOC, study day of occurrence, severity, relatedness, and outcome for each event. Non-serious unsolicited AEs will be summarized as number and percentage of subjects reporting at least one event in each MedDRA□ preferred term and SOC, cross tabulated by severity and relationship to the study device. Additionally, the proportion of subjects and exact 95% CIs of AEs in aggregate and by MedDRA□ categories will be computed.

Clinical laboratory data, including methemoglobin measurements, will be summarized by severity and as the maximum numeric value over the entire study. Graphical presentations may include box plots and shift plots.

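### Section 6.1.2 makes every abnormal laboratory value after device use an AE, so chance out-of-range results would inflate the aggregate AE proportion planned in 7.4.1

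*Combined protocol and SAP*

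**What the plan says.** Section 6.1.2, on abnormal laboratory values and findings, says: "All abnormal clinical findings or abnormal clinical laboratory tests values that occur post RD19 device use will be considered AEs". It does not define abnormal. The paragraph before it allows one repeat of an out-of-range measurement, at the investigator's judgment, where a transient cause or an error is suspected.

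Section 5.5.4, on subjects who stop using the device, is worded differently: "Any new clinically relevant finding will be reported as an AE".

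Other provisions that bear on the point:
- **Inclusion criterion 10 (4.1)** requires screening laboratory values within the laboratory's normal reference ranges.
- **Section 3.1 and the Schedule of Activities (Table 3)** place the metabolic panel, blood count with differential and urinalysis at screening and again at Day 14 or early termination.
- **Section 6.2.1** allows an abnormal laboratory finding to be an AE. It treats conditions present at screening as baseline unless they worsen.
- **Section 6.2.4** folds a laboratory abnormality that belongs to a syndrome into that diagnosis.
- **Section 7.4.1** analyses each solicited AE separately. It tabulates non-serious unsolicited AEs by preferred term, system organ class, severity and relationship, and summarises laboratory data separately. It also commits to "the proportion of subjects and exact 95% CIs of AEs in aggregate".

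The study is a single open-label arm of 25 (sections 4 and 7.2), and section 7.1 says it "is not designed to test any statistical hypotheses".

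**The concern.** A healthy subject tested on many analytes will often have one value slightly outside a reference range with nothing wrong. Under 6.1.2 that value is an AE. Because screening values had to be normal, it is nearly always new, so the baseline exclusion in 6.2.1 rarely removes it. An isolated value belongs to no syndrome, so 6.2.4 does not absorb it either.

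Such a subject then counts in the aggregate AE proportion exactly as a subject with a clinical event does. With no control arm, the study has no internal estimate of how many subjects would have had such a value without the device. A reader of the aggregate and its confidence interval cannot tell how much is reference-range background.

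The differing thresholds in 5.5.4 and 6.1.2 add a second problem: assessors could classify the same isolated value differently depending on which section they follow.

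**Working it through.** **Plan's own figure.** The documents give no expected rate of laboratory AEs, so there is nothing to reproduce on this point. The only design figures are the detection probabilities in 7.2, and nothing below depends on them.

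**Inputs from the documents.** There are 25 subjects (section 4), full completion is taken as likely (7.2), screening values are normal (4.1, criterion 10), and there is one scheduled set of panels after first device use (Table 3).

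**Assumptions, because the documents are silent.**
- Abnormal means outside a 95% reference range. 6.1.2 does not say so, but the normal reference range in criterion 10 is the only laboratory range in the available text.
- k = 14 to 40 analytes across the panels.
- Test-retest correlation ρ = 0 to 0.9.
- Between-analyte correlation r = 0 to 0.2.
- No device effect and no repeat test.

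Methemoglobin and vital signs are left out of the count.

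**Step 1: chance per analyte.** For a standard bivariate normal pair (screening X0, Day 14 X1), the probability of being out of range at Day 14, given in range at screening, is

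q = 1 − P(|X0| < 1.96 and |X1| < 1.96) / 0.95.

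**Step 2: chance per subject.** With independent analytes, P(at least one) = 1 − (1 − q)^k. For example, ρ = 0 and k = 40 give 1 − 0.95^40 = 87.1%, and 25 × 0.871 = 21.8 subjects. With r = 0.2 the probability was simulated, conditional on all k values being normal at screening.

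| ρ | r | q | k = 14 | k = 25 | k = 40 |
|---|---|---|---|---|---|
| 0 | 0 | 0.0500 | 51.2% (12.8) | 72.3% (18.1) | 87.1% (21.8) |
| 0.5 | 0 | 0.0429 | 45.9% (11.5) | 66.6% (16.6) | 82.7% (20.7) |
| 0.7 | 0 | 0.0352 | 39.5% (9.9) | 59.2% (14.8) | 76.2% (19.0) |
| 0.9 | 0 | 0.0214 | 26.2% (6.5) | 41.8% (10.5) | 58.0% (14.5) |
| 0.9 | 0.2 | simulated | 23.7% (5.9) | 36.6% (9.1) | 50.2% (12.6) |

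Expected subjects out of 25 are in brackets; q was carried unrounded. The range is about 24% to 87%, or 6 to 22 of 25.

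**Step 3: effect on the aggregate.** Suppose, for illustration only, that 30% of subjects have a clinical AE, independently of laboratory noise. The reported aggregate is 1 − (1 − 0.30)(1 − L), where L is the chance of a laboratory AE.
- Low end: 1 − 0.70 × 0.763 = 0.466, about 47%.
- High end: 1 − 0.70 × 0.129 = 0.910, about 91%.

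**Step 4: the same illustration, split.** The laboratory-only share is 0.70 × 0.237 = 0.166 at the low end and 0.70 × 0.871 = 0.610 at the high end. Added to the unchanged 0.30, these return 0.466 and 0.910. The split therefore recovers the clinical proportion without dropping any event.

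**The case against.** **Broad capture is defensible.** In a first-in-man study of 25 people, recording every abnormal value is a reasonable conservative choice, and narrowing it has a safety cost. This stands, and the fix therefore leaves capture alone.

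**The two sections do not contradict each other.** A reader might infer that 5.5.4 limits AEs to clinically relevant findings and so conflicts with 6.1.2. The text does not support that. 5.5.4 concerns subjects who stop using the device, and it does not say that other findings are not AEs. Both rules can be followed at once, and 6.2.1 leans toward the broader one. What remains is an inconsistent threshold.

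**The primary endpoint is not one pooled figure.** A reader might also infer that laboratory noise would dominate the primary AE result. The endpoint in 3.2 covers the frequency, grade and attribution of each AE. Solicited reactions have their own exact intervals, and unsolicited AEs are split by preferred term, class, severity and relationship. Only the aggregate and the laboratory-related rows are affected. Dominance cannot be derived, because the documents give neither an expected clinical AE rate nor a laboratory one.

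**The size rests on assumptions.** This also stands. An optional repeat could remove some values, although 6.1.2 does not say that a normal repeat cancels the AE. Appendix 2, which holds the grading scales, is not in the available text and may treat small deviations in a way that cannot be seen here.

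**Existing tables do not fully answer the point.** Preferred term and class rows show the laboratory events, but not how many subjects had laboratory AEs and nothing else. Attribution is a weak filter, because 6.2.9 accepts close timing alone as grounds for a related classification, and Day 14 falls within the device-use period.

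**Conclusion.** The point holds for the aggregate AE proportion, its exact 95% CI and the laboratory-related rows. If 6.1.2 is followed as written, chance out-of-range values would materially inflate the aggregate across the whole range examined. Even the most favourable case considered adds about 17 percentage points to an illustrative 30%. The exact size is not known: it depends on reading abnormal as outside a 95% reference range and on analyte counts and correlations that the documents do not give. The 5.5.4 and 6.1.2 wordings differ in threshold and need reconciling. The documents do not support a claim of outright contradiction, or a claim that the primary safety evaluation as a whole is dominated by noise.

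**What to change.** Keep full capture under 6.1.2. In 7.4.1, report the aggregate as three rows, each a proportion of subjects with an exact 95% CI:
1. subjects with at least one clinical AE;
2. subjects whose only AEs are laboratory values not forming part of a diagnosis under 6.2.4;
3. both combined, as now planned.

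The first two rows do not overlap and sum to the third. Align 5.5.4 with 6.1.2 so that one threshold applies to all subjects, and state which range abnormal refers to.

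The cost is a few words in two or three sections and one or two extra table rows. No safety data are lost.
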